4.1 Statistical design, methods, and analytical protocols

This study was a prospective, single-center, single-group target value trial.

All statistical analysis methods are described in detail in the statistical analysis plan. A first draft of the statistical analysis plan is formed after the protocol and eCRF are finalized and will be finalized prior to database locking.

4.2 Sample size calculation

4.2.1 Total sample size

This clinical trial intends to enroll 47 subjects. The sample size determination process is as follows:

This clinical study is designed for clinical verification of a single group of target values, and the tumor disease control rate, the main effectiveness evaluation index, is used as the basis for sample size estimation. According to the Guidelines for the Review of Clinical Evaluation Technologies of Proton Carbon Ion Therapy System (CFDA Circular No. 4 of 2018), the target value is set at 80%, and the bilateral significance level is 0.05, and the power degree 80%, applying the sample size estimation professional software PASS 15.0, calculated by the above parameters, the test group needs a sample size of at least 42 cases. Considering that about 10% of cases may be dropped or lost to follow-up during clinical validation, the sample size of the experimental group was expanded to 47 cases.

4.3 The level of significance and power of clinical trials

The significance level α (bilateral) = 0.05, and the power was 80%.

4.4 Expected shedding rate

In the sample size estimation process, the expected shedding rate is 10%.

This dropout rate refers to the proportion of participants who ultimately could not be included in the primary analysis. Shedding subjects are subjects who have been identified by the investigator as having serious protocol deviations. May include, but is not limited to, the following: the subject violates the inclusion criteria; Participants were not treated with experimental devices; Participants used concomitant medications/devices that are prohibited by the protocol; lack of data on key evaluation indicators; Participants did not obtain any data, etc.

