ULN	Upper Limit of Normal	Upper limit of normal value
VMAT	Volumetric-Modulated Arc Therapy	Volumetric rotational intensity-modulated radiotherapy
WBC	White Blood Cell	white blood cell
WHO	World Health Organization	World Health Organization

Protocol summary

The name of the experiment	Varian ProBeam360 Proton Therapy System China Clinical Trial (Wuhan).
Device name	proton therapy system (hereinafter referred to as ProBeam360).
Manage categories	Class III (classification: 05 radiotherapy equipment--01 radiotherapy equipment--02 medical light ion therapy system).
Scope of application	Proton therapy system provide precision radiation therapy protons for lesions, tumors, and conditions in the patient's body that require radiation therapy.
Scope of the test	Cancer patients, including tumors of intracranial, head and neck, chest, abdomen, spine, pelvis, limbs, etc
Trial design	Prospective, open-label, single-centered, single-group target value method
Trial and long-term follow-up purposes	
Clinical trial (screening-short-term follow-up): The data obtained by using Proton Beam system (ProBeam360) for radiation therapy in tumor patients compared with the target value to evaluate the effectiveness and safety of ProBeam360 for radiation therapy in tumor patients to provide clinical basis for product registration application.
 
Long-term follow-up: The long-term efficacy and safety of ProBeam360 for radiation therapy in cancer patients were evaluated by using the long-term follow-up data of ProBeam360 for radiation therapy in cancer patients.

Sample size	
At least 47 participants are enrolled in this trial.
 
Assuming the expected primary efficacy evaluation indicator (3-month tumor local control rate) is 95%, the target value is 80%, the bilateral significance level is 0.05, and the confidence level is 80%, data from 42 participants are required at the end of the 3-month observation period.
 
Considering the expected dropout rate of 10% during short-term follow-up of clinical trials, 47 subjects are required to be enrolled.
 
(1) The number of cases of tumors in the intracranial, head and neck, chest, abdomen, spine, pelvic cavity, and limbs should be evenly distributed as much as possible.
 
(2) The Intensity Modulated Proton Therapy (IMPT) technology and exercise management system should be used and validated in this study.

clinical trial	
Number of institutions	1 site

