Evaluation method: The changes in tumor CT or MRI imaging before and after treatment were evaluated by an independent imaging review panel according to RECIST 1.1. At 3 months of radiographic evaluation, if PD is found, PET-CT is required to confirm it.

Calculation formula: DCR = number of disease control subjects / total number of subjects \times 100%.

Criteria: See RECIST 1.1 for details. At the time of 3-month imaging evaluation, if the patient is found to have PD, PET-CT examination is required to confirm it, if progress is confirmed, it is recorded as PD, if progress cannot be confirmed, it may

be false progression, and it is recorded as SD. If prostate cancer does not have biochemical recurrence, PET-CT examination is not required, and there is no metastasis by default, which is regarded as tumor control, and if biochemical recurrence occurs, it is regarded as tumor not controlled, and PET-CT is required to confirm tumor metastasis.

Note: Participants who aborted the trial for any reason (except loss to follow-up) before the end of the last radiation therapy were considered to have disease progression (PD) or were not controlled. Disease site evaluation uses the same approach as baseline, including consistent contrasted/non-contrast scans and prompt scanning. If changes are needed, the case must be discussed with a radiologist to determine whether an alternative approach is possible. If not, the objective situation in the future is unclear.

3.1.4.2 Secondary effectiveness evaluation indicators and their methods and timing of evaluation, recording, analysis

(1) Objective response rate (ORR).

Reason for selection: The Guidelines for the Review of Clinical Evaluation Technologies of Proton Carbon Ion Therapy Systems (CFDA Circular No. 4 [2018]) recommends the use of the latest version of the commonly used evaluation criteria for radiation oncology as the clinical trial evaluation criteria, so RECIST 1.1 is used. Relevant indicators as effectiveness evaluation criteria; Due to the particularity of the disease, the evaluation method recommended in the relevant diagnosis and treatment guidelines is selected. All of them can directly measure the effect of radiotherapy and are widely recognized and applied by clinicians.

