4.7.1 Data statistical methods

Statistical analysis with SAS 9.4 software.

All data are described statistically, including demographics, baselines, all efficacy measures, and all safety data. The measurement data give the mean, standard deviation, minimum, maximum, median, 25th quantile and 75th quantile; The counting data gives the frequency and the corresponding percentage.

Effectiveness Analysis:

The number and percentage of cases achieving DCR were calculated, and the Clopper-Pearson method was used to calculate the 95% confidence interval for tumor disease control rate. ORR was calculated and the Clopper-Pearson method was used to calculate the objective response rate 95% confidence interval. Descriptive statistics on the percentage change from baseline of the sum of the longest diameter (SLD) of the measurable tumor. The Waterfall Chart was made by the maximum percentage reduction in SLD per patient compared to the screening period.

The *Kaplan-Meier* method was used to calculate the median duration of response, median progression-free survival, median survival, and overall survival, and plotted *K-M* curves (long-term follow-up data).

For tumor markers, compare and evaluate the changes before and after treatment, and give clinical evaluation [no clinical significance, clinically significant (tend to normal), clinically significant (tend to be abnormal), not checked].

Safety Analysis:

Descriptive statistics were used to classify organ systems in MedDRA medical terms, and the incidence, occurrence, and severity of adverse events, adverse reactions, and serious adverse events were summarized.

Laboratory indicators, ECOG physical status classification and other safety-related indicators were compared and evaluated before and after treatment, and clinical evaluation ([no clinical significance, clinically significant (tending to normal), clinically significant (tending to abnormal), not checked], CTCAE grade evaluation before and after treatment cross-table.

4.7.2 Missing, unused, or erroneous data (including mid-exit and evacuation) and unreasonable data

All missing, unused or erroneous data (including mid-exit and withdrawal) and unreasonable data will be discussed and finalized by investigators and

biostatisticians during the blinding review phase. The basic statistical principles of these data processing are as follows:

- (1) Describe the details of each shedding case;
- (2) Missing data from baseline, which can not be estimated;

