- (3) The missing values of DCR and primary safety evaluation indicators (proportion of CTCAE grade 3 toxicities, proportion of CTCAE grade 4 and 5 toxicities) at 3 months after the end of treatment can be estimated using worst-case scenarios.
- (4) The missing values of qualitative secondary effectiveness evaluation indicators ORR, DCR and long-term follow-up effectiveness evaluation indicators can be estimated using worst-case scenarios;
- (5) The missing values of quantitative secondary efficacy evaluation indicators DOR, tumor markers, product ease assessment and long-term follow-up effectiveness evaluation indicators were not estimated.
- (6) Erroneous, unreasonable data (out-of-range data and data that contradicts other data or indicators of the study protocol) can be treated as missing values;
- (7) Worst-case estimates are used for missing values for all minor safety indicators;

- (8) The sensitivity analysis of the main effectiveness evaluation indicators and main safety evaluation indicators after treatment was carried out in the whole analysis center.
- (9) The sensitivity analysis of all secondary effectiveness evaluation indicators after treatment was carried out in the whole analysis center.
- (10) For all secondary safety evaluation indicators after treatment, sensitivity analysis was carried out in the security dataset.

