4.9 Selection criteria and rationale for participants included in the analysis

Full Analysis Set (FAS): All subjects who received at least 1 investigational device treatment and at least one post-baseline observation data will be enrolled in FAS, according to the basic principles of intention-to-treat analysis. FAS will be used as the primary population for baseline data and sensitivity analysis for validity evaluation. Participants may only be excluded in very limited circumstances, including when important inclusion criteria are violated and no observational data are available after enrollment.

Compliant protocol set (PPS): is a subset of FAS, defined as subjects who have measurable lesions at baseline and have completed at least one assessment of primary efficacy indicators after baseline. PPS will be the primary population for the effectiveness evaluation of this study.

Safety dataset (SS): all participants who received at least 1 study device treatment and at least one safety assessment. SS will be the primary population for safety analysis in this study.

The assessment of baseline characteristics will use the full set of analyses; The evaluation of effectiveness will use both the full analysis set and the conforming protocol set; Security analysis uses security datasets.

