5.3.2 Deviation from the protocol

Depending on protocol deviations and the specific situation, participants who are not included in FAS, PPS, or SS will be discussed at the data review meeting and identified prior to database locking.

The number, number and incidence of protocol deviations in each category are summarized and the list details the regimen deviations of the subjects.

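### The protocol and SAP do not agree on who is in the primary DCR analysis, and with exactly four failures one exclusion reverses the efficacy result

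*Protocol*

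**What the plan says.** - **Protocol 4.4 (dropout allowance).** The 10% is the share of participants who end up outside the primary analysis. The section continues: "Shedding subjects are subjects who have been identified by the investigator as having serious protocol deviations". Its examples are expressly not exhaustive: breach of the inclusion criteria, no device treatment, prohibited concomitant medication or devices, missing key data, no data at all.
- **Protocol 4.9 (analysis sets).** The PPS is a subset of the FAS, "defined as subjects who have measurable lesions at baseline and have completed at least one assessment of primary efficacy indicators after baseline". It is the primary population for effectiveness. SAP 3 gives the same definition. Neither mentions protocol deviations.
- **SAP 5.3.2 (deviations).** Depending on deviations and the circumstances of the case, "participants who are not included in FAS, PPS, or SS will be discussed at the data review meeting" and identified before database lock. No criteria are listed.
- **Protocol 3.1.4.1, Note.** Participants who stopped the trial for any reason except loss to follow-up "before the end of the last radiation therapy were considered to have disease progression (PD") or not controlled.
- **SAP 5.6.** If FAS and PPS conclusions differ, the PPS is the main one, and the differences are to be discussed and explained.
- **Protocol 4.5, with 4.7.1 and SAP 5.4.1.** The efficacy target is reached if the lower limit of the Clopper-Pearson 95% interval exceeds 80%.

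**The concern.** Take a subject who was treated, had a measurable lesion, was read at 3 months, and has a deviation judged serious. Under 4.9 and SAP 3 this subject is in the primary analysis. Under 4.4 the subject is out. SAP 5.3.2 shows that deviation-based exclusion is meant to operate in practice, but gives no rule for it. The trial is open-label with a single group, and nothing requires membership to be settled by people unaware of the response.

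Aborted subjects raise a second, separate problem. The endpoint rule makes them failures. If they have no post-baseline efficacy assessment, the PPS definition removes them, so an outcome that the protocol has already assigned never reaches the primary denominator. This route can only remove failures.

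There is no control arm, so the efficacy conclusion rests on one count against a fixed limit. A change of one subject in the denominator can decide it, and the FAS does not overrule the PPS.

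**Working it through.** **Inputs.** Protocol 4.3: "The significance level α (bilateral) = 0.05, and the power was 80"%. Protocol summary: "Assuming the expected primary efficacy evaluation indicator (3-month tumor local control rate) is 95%, the target value is 80"%. Protocol 4.2.1: 42 evaluable, 47 enrolled. Protocol 4.4: 10% dropout. Pass rule as in Protocol 4.5.

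**Step 1: reproduce the plan's sample size.** One-sample proportion, normal approximation:

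n = [(1.960 × √(0.80 × 0.20) + 0.842 × √(0.95 × 0.05)) / (0.95 − 0.80)]² = 41.59, so 42.

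42 / 0.90 = 46.67, so 47. Both stated figures reproduce. The allowance is 47 − 42 = 5 subjects outside the primary analysis.

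**Step 2: what the pass rule allows.** With x controlled of n, the lower limit is the 2.5% quantile of a Beta(x, n − x + 1) distribution. For every n from 42 to 47 the limit exceeds 80% with 3 failures and not with 4.

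| Controlled / n | Failures | Lower limit | Criterion |
|---|---|---|---|
| 44/47 | 3 | 82.46% | met |
| 43/47 | 4 | 79.62% | missed |
| 43/46 (one failure removed) | 3 | 82.10% | met |
| 38/42 | 4 | 77.38% | missed |
| 38/41 (one failure removed) | 3 | 80.08% | met |

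A single removal therefore changes the result only when there are exactly 4 failures, and it does so for each starting n from 42 to 47.

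**Step 3: how often that happens.** P(exactly 4 failures of 47) is P(at most 4) − P(at most 3).

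- True DCR 95%: 0.9155 − 0.7926 = 0.123 (12.3%).
- True DCR 80%: 0.0287 − 0.0093 = 0.019 (1.9%).

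**Step 4: chance of meeting the criterion at a true DCR of 80%.** The nominal one-sided level is 2.5%. If up to e failures can be removed from 47, the criterion is met with at most 3 + e failures.

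| Situation | Chance of meeting the criterion |
|---|---|
| No exclusions, n = 47 | 0.9% |
| Five exclusions unrelated to outcome, n = 42 | 2.1% |
| One failure removable from 47 | 2.9% |
| Two failures removable from 47 | 7.0% |

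The last two rows are upper bounds: they assume that every exclusion falls on a failure whenever that helps.

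**Step 5: the aborted subject.** Suppose one of 4 failures among 47 aborted before the end of radiotherapy, was not lost to follow-up, and had no post-baseline efficacy assessment. Protocol 3.1.4.1 gives 43/47 (missed). The PPS definition gives 43/46 (met). No one has exercised discretion; two sections simply give different answers.

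**The case against.** **4.4 is a planning passage.** It explains the inflation from 42 to 47, the sets are defined elsewhere, and the SAP does not repeat the investigator clause. Most of its examples overlap the FAS and PPS definitions. This stands in part: the new elements are prohibited concomitant treatment and the open-ended class of serious deviations. But SAP 5.3.2 also ties set membership to deviations, without criteria, so the conflict is not confined to sample-size text.

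**A reader might infer that the investigator alone may remove known failures.** The documents do not show this. Exclusions go to a meeting, and response is read by an independent imaging panel, with a third reader settling disagreements (SAP 5.4.1). Whether those deciding will know the reads is not stated. Knowledge of outcome is possible and not prevented; it is not established.

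**A reader might cite larger error rates.** If all five planned dropouts were failures removed from the analysis, the chance of meeting the criterion at a true 80% would be 38%. That requires deliberate selection, and nothing in the plan supports assuming it. Outcome-neutral exclusions leave the rate at 2.1%, under the nominal level.

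**A reader might lean on two phrases in Protocol 4.7.2.** The reference to "biostatisticians during the blinding review phase" concerns missing and erroneous data, not set membership. The rule that bad data "can be treated as missing values" is limited to out-of-range or contradictory values, so it is not a general means of discarding a panel reading.

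**An exclusion would be visible.** Dropouts are described case by case, deviations are listed, and FAS results are reported. This stands, but visibility does not change which set decides. The FAS safeguard is itself unclear: SAP 4.3 leaves missing primary values unfilled in the FAS, while SAP 5.4.1 fills them by worst observation carried forward.

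**Conclusion.** The concern holds as a conflict over the primary analysis population, together with a separate conflict over aborted subjects. As written, the same data can give two primary DCRs, and SAP 5.6 gives precedence to the set whose membership is unclear.

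The consequence is narrow but realistic. One excluded failure reverses the efficacy result only at exactly 4 failures, a count with about a one in eight chance if the device performs as planned. For a device truly at the 80% target, the error rate stays below 2.5% without targeted removal. It reaches at most 2.9% or 7.0% if one or two failures can be removed.

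These figures assume independent subjects with a common DCR, 47 subjects before exclusions (42 for the outcome-neutral case), and the confidence-limit rule of Protocol 4.5. They concern efficacy only. The grade 3 and grade 4/5 criteria use the safety set and can still fail the trial, so a reader should not infer that one exclusion would turn an overall failure into an overall pass.

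**What to change.** 1. **One closed PPS rule.** State it identically in Protocol 4.9 and SAP 3, with any deviation-based exclusions listed in advance. Limit 4.4 to explaining the 10% inflation. In SAP 5.3.2, remove the circumstances of the individual case as a ground for exclusion.
2. **Aborted subjects.** Keep in the primary DCR denominator, as not controlled, everyone who aborted before the end of radiotherapy other than by loss to follow-up, with or without a post-baseline assessment. This applies the existing rule in 3.1.4.1 and leaves its exception intact.
3. **Who decides membership.** Have it decided and documented before database lock by people without access to response results. Holding back the panel's reads from the site would not achieve this: the radiotherapist also evaluates efficacy (Protocol 3.1.3), and progression found at 3 months needs PET-CT confirmation (3.1.4.1).

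The cost is wording in both documents and the organisation of the review meeting. No extra subjects or procedures are needed. The downside is that the DCR may be slightly less favourable.

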4.5 Criteria for passing/failing clinical trial results

The target value of the main effectiveness evaluation index (tumor disease control rate) of the trial was 80%, and if the lower limit of the 95% confidence interval of the test results was greater than 80%, the tumor disease control rate of the experimental group reached the target.

If the main safety evaluation index of the trial (the proportion of CTCAE grade 3 toxic reactions) is greater than 5%, the clinical trial fails.

If the trial has CTCAE grade 4 and 5 toxicity, the clinical trial fails.

4.6 Criteria and reasons for terminating trials on statistical grounds

No interim analysis was performed in this study and therefore criteria for termination of the trial for statistical reasons were not established.

4.7 Statistical methods of data, together with methods of dealing with missing, unused or erroneous data and irrational data

4.7.1 Data statistical methods

Statistical analysis with SAS 9.4 software.

All data are described statistically, including demographics, baselines, all efficacy measures, and all safety data. The measurement data give the mean, standard deviation, minimum, maximum, median, 25th quantile and 75th quantile; The counting data gives the frequency and the corresponding percentage.

Effectiveness Analysis:

The number and percentage of cases achieving DCR were calculated, and the Clopper-Pearson method was used to calculate the 95% confidence interval for tumor disease control rate. ORR was calculated and the Clopper-Pearson method was used to calculate the objective response rate 95% confidence interval. Descriptive statistics on the percentage change from baseline of the sum of the longest diameter (SLD) of the measurable tumor. The Waterfall Chart was made by the maximum percentage reduction in SLD per patient compared to the screening period.

The *Kaplan-Meier* method was used to calculate the median duration of response, median progression-free survival, median survival, and overall survival, and plotted *K-M* curves (long-term follow-up data).

For tumor markers, compare and evaluate the changes before and after treatment, and give clinical evaluation [no clinical significance, clinically significant (tend to normal), clinically significant (tend to be abnormal), not checked].

Safety Analysis:

Descriptive statistics were used to classify organ systems in MedDRA medical terms, and the incidence, occurrence, and severity of adverse events, adverse reactions, and serious adverse events were summarized.

Laboratory indicators, ECOG physical status classification and other safety-related indicators were compared and evaluated before and after treatment, and clinical evaluation ([no clinical significance, clinically significant (tending to normal), clinically significant (tending to abnormal), not checked], CTCAE grade evaluation before and after treatment cross-table.

4.7.2 Missing, unused, or erroneous data (including mid-exit and evacuation) and unreasonable data

All missing, unused or erroneous data (including mid-exit and withdrawal) and unreasonable data will be discussed and finalized by investigators and

biostatisticians during the blinding review phase. The basic statistical principles of these data processing are as follows:

- (1) Describe the details of each shedding case;
- (2) Missing data from baseline, which can not be estimated;
- (3) The missing values of DCR and primary safety evaluation indicators (proportion of CTCAE grade 3 toxicities, proportion of CTCAE grade 4 and 5 toxicities) at 3 months after the end of treatment can be estimated using worst-case scenarios.
- (4) The missing values of qualitative secondary effectiveness evaluation indicators ORR, DCR and long-term follow-up effectiveness evaluation indicators can be estimated using worst-case scenarios;
- (5) The missing values of quantitative secondary efficacy evaluation indicators DOR, tumor markers, product ease assessment and long-term follow-up effectiveness evaluation indicators were not estimated.
- (6) Erroneous, unreasonable data (out-of-range data and data that contradicts other data or indicators of the study protocol) can be treated as missing values;
- (7) Worst-case estimates are used for missing values for all minor safety indicators;

- (8) The sensitivity analysis of the main effectiveness evaluation indicators and main safety evaluation indicators after treatment was carried out in the whole analysis center.
- (9) The sensitivity analysis of all secondary effectiveness evaluation indicators after treatment was carried out in the whole analysis center.
- (10) For all secondary safety evaluation indicators after treatment, sensitivity analysis was carried out in the security dataset.

